5.7 Subject Replacement Strategy

The phase II expansion dose will treat up to 35 patients evaluable for response to therapy (20 in the first stage, then if at least 2 responses are seen, an additional 15 patients). If patients become ineligible prior to starting therapy or for some other reason fail to be evaluable for response assessment, additional patients will be treated in their place.

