2.0 TRIAL DESIGN

2.1 Introduction

This is a Phase I/II, non-randomized, open-label, interventional study of Pembrolizumab combined with doxorubicin for patients with advanced sarcoma. Most patients will receive this as front line therapy. As a rule, the trial is generally inclusive for most sarcoma subtypes. However, it excludes patients with prior anthracycline treatment. Patients with Ewings Sarcoma, Osteosarcoma, and some Rhabdomyosarcomas are excluded as these histologic sarcoma subtypes have well-established, evidence-based treatment paradigms combining anthracyclines with other chemotherapy.

The Phase I stage will evaluate two dose levels of doxorubicin (45 and 75 mg/m²) combined with Pembrolizumab. The 75 mg/m² doxorubicin dose is widely considered standard of care for sarcoma, as is being used as the “control” arm for recent and on-going phase III trials (NCT02451943) (Judson, Verweij et al. 2014). All patients will receive Pembrolizumab at the flat dose of 200 mg given intravenously every 3 weeks. Unless serious adverse events are observed, the Phase II expansion will combine the 75 mg/m² dose of doxorubicin with Pembrolizumab.

The phase II portion will use a two stage design treating an initial 20 patients with the combination of Doxorubicin and Pembrolizumab. If two or more objective responses are seen (either complete or partial responses), an additional 15 patients will be treated for a total of 35 patients. In summary, we expect that 44 patients will be treated on the trial (9 in the phase I portion and 35 on the phase II portion). If an additional 3 patients needed to be treated in the initial phase I cohort this could potentially increase to a maximum enrollment of 47.

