2.2 Dosing Schedule

In order to “prime” the immune system prior to combination therapy, patients will receive one cycle of Pembrolizumab as a single agent before starting the combination of doxorubicin and Pembrolizumab. Patients will receive a maximum of 6 cycles of doxorubicin. After this, patients with clinical benefit may continue on study with single agent Pembrolizumab.

Pembrolizumab has been given q2 weeks and q3 weeks and the optimal schedule is unclear. However, it is approved by the FDA for use every 3 weeks, and this dosing will also minimize the necessary infusion center visits. Patients will receive Pembrolizumab and doxorubicin sequentially at the same infusion center visit. Doxorubicin will be given first.

Patients with SD, PR or CR may continue to take Pembrolizumab for 2 years (and no more than 35 cycles). After this, they must discontinue Pembrolizumab. If the patient had been responding prior to discontinuation and they immediately progress 8-12 weeks after discontinuation, they may then resume pembrolizumab for one year or until progression.

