2.4 Assessment of Response

Response assessment will be based on RECIST 1.1. Patients with clinical benefit (SD, PR, CR) after 6 cycles of doxorubicin will continue on single agent Pembrolizumab until confirmed progression RECIST, severe toxicity (see **Section 5**), or 2 years of therapy whichever comes first. Patients who receive a CR will be treated until they have had at least 24 weeks of treatment and have been treated for at least 2 cycles after their CR was declared. Patients who are able to be brought to a CR surgically should be treated just as if they had a CR in response to the medication. Patients confirmed to have a CR who have been taken off treatment will continued to be monitored radiographically every 12 weeks. Upon relapse they can be re-treated with Pembrolizumab for up to one year.

While, all patients will start therapy with unresectable/metastatic disease, it is possible that a responding patient becomes surgically resectable so that they have no evidence of disease. These patients may undergo surgery and afterwards should be followed as if they had a CR, with the rules regarding progression and restarting treatment.

Patients will have their first post-treatment scan after 3 cycles of doxorubicin, prior to receiving their fourth cycle of doxorubicin. Patients with PR or SD will have their second post treatment scan 3-6 weeks after their last (sixth) cycle of doxorubicin. Responses will be determined by RECIST 1.1. After 6 cycles of doxorubicin have been completed and Pembrolizumab is being given as a single agent, scans will be performed every 12 weeks (+/- 1 week) until progression.

Subjects with an *unconfirmed* progression of disease may discontinue but will be encouraged to continue trial treatment until progression is confirmed following two additional cycles of therapy or until disease progression becomes symptomatic. However, subjects may only receive study treatment while waiting for confirmation of PD if the following criteria are met:

- No decline in ECOG performance status
- Absence of rapid progression of disease
- Absence of progressive tumor at critical anatomical sites (e.g. cord compression) requiring urgent alternative medical intervention

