2.6 Phase II extension

[figure not shown]
The phase II extension will use a SWOG 2-stage design (modified Simon's 2 stage design) in order to detect a response rate (CR + PR) of 35%. This is based on a predicted overall response rate for single agent doxorubicin of 15%. 20 patients will be treated in the first stage. If 2 or more patients have CR or PR, an additional 15 patients will be treated. If at least 10 CR or PR's are seen, this will be considered a positive study. Patients treated in the phase I portion of the study will not be included in the phase II analysis. Any toxicity defined as a DLT for the phase I portion will also trigger a meeting of the DSMB during the phase II portion of the trial. Should 2 of these events occur, enrollment must halt until the DSMB meets.

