3.0 OBJECTIVES & HYPOTHESES

3.1 Primary Objectives & Hypotheses

3.1.1 Objective: To assess the safety and tolerability of the combination of Pembrolizumab and Doxorubicin in patients with advanced soft tissue sarcoma (STS).

Hypothesis: The combination of Doxorubicin and Pembrolizumab will be similar to the toxicity of standard Doxorubicin and Pembrolizumab therapy when these drugs are used as single agents.

3.1.2 Objective: To assess the clinical response rate of advanced soft tissue sarcoma (STS) patients receiving the combination of Pembrolizumab and Doxorubicin.

Hypothesis: The addition of Pembrolizumab to Doxorubicin will result in a 20% increase in the objective response rate (CR + PR) compared with historical controls.

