5.6 Subject Withdrawal/Discontinuation Criteria

Subjects may withdraw consent at any time for any reason or be dropped from the trial at the discretion of the investigator should any untoward effect occur. In addition, a subject may be withdrawn by the investigator or the Sponsor-Investigator if enrollment into the trial is inappropriate, the trial plan is violated, or for administrative and/or other safety reasons. A subject will be considered withdrawn and no longer followed if they enroll onto hospice care. Specific details regarding discontinuation or withdrawal are provided in Section 7.1.4 – Other Procedures.

A subject must be discontinued from the trial for any of the following reasons:

- The subject or legal representative (such as a parent or legal guardian) withdraws consent.
- Confirmed radiographic disease progression

Note: For unconfirmed radiographic disease progression, please see Section 5.2.2

- Unacceptable adverse experiences as described in Section 5.2.1.2

- Intercurrent illness that prevents further administration of treatment
- Investigator's decision to withdraw the subject
- The subject has a confirmed positive serum pregnancy test
- Noncompliance with trial treatment or procedure requirements
- The subject is lost to follow-up
- Completed 24 months of uninterrupted treatment with pembrolizumab or 35 administrations of study medication, whichever is later.

Note: 24 months of study medication is calculated from the date of first dose. Subjects who stop pembrolizumab after 24 months may be eligible for up to one year of additional study treatment if they progress after stopping study treatment provided they meet the requirements detailed in Section 7.1.5.5

- Administrative reasons

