Pregnancy Test – Urine or Serum (in appropriate study subjects)	X	X	X	X	X	X	X	X	X	X	X	X	X	X	
PT/INR and aPTT	X														
CBC with Differential	X	X	X	X	X	X	X	X	X	X	X	X	X	X	
Comprehensive Serum Chem Panel	X	X	X	X	X	X	X	X	X	X	X	X	X	X	
Urinalysis	X														

Trial Period:	Screening	Pembro Only	Doxorubicin/Pembrolizumab Combination							Pembrolizumab Only (repeat)				End of Treatment	
Treatment Cycle/Title:	Screening	1	2	3	4	5	6	7	8	9	10	11	At time of Discon	30 days post discon	
Scheduling Window (Days):	see section 7.1.5	± 3	± 3	± 3	± 3	± 3	± 3	± 3	± 3	± 3	± 3	± 3	± 7	± 7	
T3, FT4 and TSH	X	X	X	X	X	X	X	X	X	X	X	X	X	X	
Tumor Imaging ¹	X			X					X						
Archival Tissue Collection (slides)	X														
Correlative Studies Blood Collection	X	X	X			X			X				X		

1: Tumor imaging may be performed with a +/- 1-week window. Scans will take place per the schedule even if there are treatment delays.

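### Section 5.7 lets treated but non-evaluable phase II patients be replaced, while the protocol text neither defines evaluable nor says how an unassessed treated patient counts in the primary response rate

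*Combined protocol and SAP*

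**What the plan says.** Section 5.7 describes the phase II numbers (20, then 15 more) as patients evaluable for response. It provides for replacement on two grounds: becoming ineligible before starting therapy, or, in its words, "for some other reason fail to be evaluable for response assessment, additional patients will be treated in their place". Only the first ground is tied to the time before treatment.

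The design sections count differently. Section 2.1 says "an additional 15 patients will be treated for a total of 35 patients", and Section 2.6 says "20 patients will be treated in the first stage". Section 8.2 sets the success rule at 10 responses out of 35 patients. The only patients it excludes from the phase II analysis are those from phase I. It names no analysis set and gives no rule for a missing response assessment.

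Three other passages bear on who could be non-evaluable:

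- Section 2.2: "patients will receive one cycle of Pembrolizumab as a single agent before starting the combination of doxorubicin and Pembrolizumab". Section 3.1.2 puts the response question for "patients receiving the combination of Pembrolizumab and Doxorubicin". The plan does not say whether a patient who receives only the priming cycle counts.
- Section 2.4: "Patients will have their first post-treatment scan after 3 cycles of doxorubicin, prior to receiving their fourth cycle of doxorubicin". Section 6.1 adds that "Tumor imaging may be performed with a +/- 1-week window".
- Section 5.6: "A subject will be considered withdrawn and no longer followed if they enroll onto hospice care".

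**The concern.** ORR is the phase II primary endpoint. It is judged in one open-label arm by a fixed count against a fixed historical 15%, so no control arm absorbs a change of denominator.

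Patients who leave before the first scan are plausibly mostly non-responders. Replacing them puts in their place patients who reached a scan, so the observed ORR rises relative to an all-treated rate with no drug effect. Both the 2-of-20 gate and the 10-of-35 rule are exposed. Because evaluable is undefined, the decision to replace can also be taken once a patient's course is known.

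**Working it through.** **Inputs from Section 8.2.** Null ORR 15%, one-sided 0.05 level, 85% power at 35%; 20 patients, continue if at least 2 respond; 35 in total, success if at least 10 respond.

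**Assumed, not in the documents.** The fraction q of treated patients who are replaced; how often they would have responded; whether 15% and 35% are rates per treated or per evaluable patient.

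**Formula.** With p the response rate among counted patients,

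P(success) = Σ over x = 2 to 20 of P[Bin(20, p) = x] × P[Bin(15, p) ≥ max(0, 10 − x)].

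**1. The plan's own figures.** At p = 0.15 the result is 0.0292; at p = 0.35 it is 0.8348, within two points of the stated 85%. A cut-off of 9 would give 0.0688 under the null, so 10 is the smallest cut-off that holds 0.05.

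**2. The window.** Cycle 1 (pembrolizumab alone) is week 0. Doxorubicin doses 1 to 4 fall at weeks 3, 6, 9 and 12. Under Section 2.4 the first scan is therefore at about week 12. The imaging row of the Section 6.1 flow chart, as extracted, marks cycle 3 (about week 6). That may be an extraction fault and nothing here rests on it, but an earlier scan would shorten the window.

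**3. Type I error under replacement, if 15% is an all-treated rate.**

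- No replaced patient would have responded: 0.15 = p(1 − q), so p = 0.15/(1 − q).
- Replaced patients would have responded at half the others' rate: 0.15 = p(1 − q) + 0.5pq, so p = 0.15/(1 − 0.5q).

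| q | p, none respond | Type I error | p, half rate | Type I error |
|---|---|---|---|---|
| 0 | 0.150 | 2.9% | 0.150 | 2.9% |
| 5% | 0.158 | 4.0% | 0.154 | 3.4% |
| 10% | 0.167 | 5.5% | 0.158 | 4.0% |
| 20% | 0.188 | 10.5% | 0.167 | 5.5% |

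The 5% level is passed at about q = 8.5% in the first case and about q = 17% in the second.

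**4. If 15% is an evaluable-only rate.** Counted patients respond at 0.15 whatever q is, and type I error stays at 2.9%.

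**5. The same in counts, if no replaced patient responded.** Ten responses in 35 is 28.6%, with P(X ≥ 10) = 0.029 at a 15% rate. With three replaced it is 10/38 = 26.3%, P = 0.0495. With four it is 10/39 = 25.6%, P = 0.058.

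**6. Counting all 35 treated patients, unassessed as non-responders.**

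- Both rates all-treated: type I error 2.9% and power 83.5%, unchanged.
- Both rates evaluable-only: the rates per treated patient become 0.15(1 − q) and 0.35(1 − q). Type I error is 2.1% at q = 5% and 1.5% at 10%. Power is 77.6% and 70.5%.

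**7. Numbers treated under Section 5.7 as written.** On average 35/(1 − q): 36.8 at q = 5% and 38.9 at q = 10%. The maximum enrollment of 47 in Section 2.1 equals 12 + 35 and leaves no room for these extra patients.

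**The case against.** The strongest case is that the harm is conditional at every step. The documents give no replaced fraction, no response rate in replaced patients and no denominator for the historical 15%. If the 15% was measured in evaluable patients, Section 5.7 matches its benchmark and nothing is inflated. The rule also has slack, spending 2.9% of a 5% allowance. Even in the worst case modelled, about three patients must be replaced before that is used up. All of this stands, and the figures are illustrations only.

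The affected group is also narrower than the wording of Section 5.7 suggests. Measurable disease is required at entry, Section 6.1 keeps scans on schedule despite treatment delays, and Section 5.6 continues disease follow-up for patients who stop for reasons other than progression. A stop for toxicity alone therefore need not make a patient non-evaluable. What remains is death, hospice, withdrawal of consent, loss to follow-up or new therapy before the first scan. Replacing patients who never start treatment is unobjectionable.

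RECIST 1.1 is adopted by reference, so the claim is limited to what the protocol text states. Defining evaluable in advance and restricting the reasons for replacement would also close the gap in wording. It would still leave early losses outside the denominator, unless the permitted reasons were confined to patients never treated.

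A reader might infer that Sections 2.1 and 2.6 contradict Section 5.7. The documents do not establish that, because the passages can be read together as 35 evaluable patients, all of whom are treated.

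**Conclusion.** The concern holds as a missing definition combined with an operative replacement rule that reaches treated patients. Followed as written, the plan allows early losses to leave the denominator of the primary endpoint, and the likely direction is a higher observed ORR than an all-treated rate.

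A reader might go further and infer that the test breaches its 0.05 level. The documents do not support this. A breach requires that 15% is an all-treated rate and also that about 8.5% of treated patients are replaced with none a would-be responder, or about 17% if they would have responded at half the others' rate. If 15% is an evaluable-only rate, type I error stays at 2.9%.

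Inflation under the current rule and loss of power under the fix do not both arise when 15% and 35% share a denominator. Section 3.1.2 suggests they do, since it frames the target as a 20% increase over historical controls. The point should be fixed because the remedy is short and the primary denominator should not be open.

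**What to change.** In Sections 5.7 and 8.2:

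- Make the primary ORR set all phase II patients who start study treatment. State in advance whether that means the priming dose or the first combination dose, since this decides whether a patient who receives only the priming cycle counts.
- Count patients in that set without a post-baseline RECIST 1.1 assessment as non-responders.
- Replace only patients who never start study treatment, on the same definition.
- Keep the 2-of-20 and 10-of-35 rule on that set.
- Define response-evaluable and report the ORR in those patients as a sensitivity analysis.
- State whether 15% and 35% are all-treated or evaluable-only rates.

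The cost is a few sentences and possibly a lower reported ORR. If both rates are all-treated, type I error stays at 2.9% and power at 83.5%. If both are evaluable-only, type I error does not rise, but power falls to 77.6% with 5% non-evaluable and 70.5% with 10%. That loss should be stated in the plan rather than met by adding patients.

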5.8 Clinical Criteria for Early Trial Termination

Early trial termination will be the result of the criteria specified below:

1. Quality or quantity of data recording is inaccurate or incomplete
2. Poor adherence to protocol and regulatory requirements
3. Incidence or severity of adverse drug reaction in this or other studies indicates a potential health hazard to subjects

4. Plans to modify or discontinue the development of the study drug

In the event of Merck decision to no longer supply study drug, ample notification will be provided so that appropriate adjustments to subject treatment can be made.

6.0 TRIAL FLOW CHART

6.1 Study Flow Chart

Trial Period:	Screening	Pembro Only	Doxorubicin/Pembrolizumab Combination							Pembrolizumab Only (repeat)				End of Treatment	
Treatment Cycle/Title:	Screening	1	2	3	4	5	6	7	8	9	10	11	At time of Discon	30 days post discon	
Scheduling Window (Days):	see section 7.1.5	± 3	± 3	± 3	± 3	± 3	± 3	± 3	± 3	± 3	± 3	± 3	± 7	± 7	

Trial Period:	Screening	Pembro Only	Doxorubicin/Pembrolizumab Combination							Pembrolizumab Only (repeat)				End of Treatment	
Treatment Cycle/Title:	Screening	1	2	3	4	5	6	7	8	9	10	11	At time of Discon	30 days post discon	
Scheduling Window (Days):	see section 7.1.5	± 3	± 3	± 3	± 3	± 3	± 3	± 3	± 3	± 3	± 3	± 3	± 7	± 7	
Informed Consent	X														
Inclusion/Exclusion Criteria	X														
Demographics and Medical History	X														
Prior and Concomitant Medication Review	X														
Trial Treatment															

Trial Period:	Screening	Pembro Only	Doxorubicin/Pembrolizumab Combination							Pembrolizumab Only (repeat)				End of Treatment	
Treatment Cycle/Title:	Screening	1	2	3	4	5	6	7	8	9	10	11	At time of Discon	30 days post discon	
Scheduling Window (Days):	see section 7.1.5	± 3	± 3	± 3	± 3	± 3	± 3	± 3	± 3	± 3	± 3	± 3	± 7	± 7	
Administration															
Post-study anticancer therapy status													X	X	
Survival Status													X	X	
Review Adverse Events		X	X	X	X	X	X	X	X	X	X	X	X	X	
Full Physical Examination	X														
Directed Physical Examination		X	X	X	X	X	X	X	X	X	X	X	X	X	
Vital Signs and	X	X	X		X			X	X		X	X	X	X	

Trial Period:	Screening	Pembro Only	Doxorubicin/Pembrolizumab Combination							Pembrolizumab Only (repeat)				End of Treatment	
Treatment Cycle/Title:	Screening	1	2	3	4	5	6	7	8	9	10	11	At time of Discon	30 days post discon	
Scheduling Window (Days):	see section 7.1.5	± 3	± 3	± 3	± 3	± 3	± 3	± 3	± 3	± 3	± 3	± 3	± 7	± 7	
Weight				X		X	X			X					
ECOG Performance Status	X	X	X	X	X	X	X	X	X	X	X	X	X	X	
EKG (Phase I portion)	X		X	X	X	X	X	X					X	X	
EKG (Phase II portion)	X		X			X							X	X	
Echo/MUGA (phase I)	X				X										
Echo/MUGA (phase II)	X														

Trial Period:	Screening	Pembro Only	Doxorubicin/Pembrolizumab Combination							Pembrolizumab Only (repeat)				End of Treatment	
Treatment Cycle/Title:	Screening	1	2	3	4	5	6	7	8	9	10	11	At time of Discon	30 days post discon	
Scheduling Window (Days):	see section 7.1.5	± 3	± 3	± 3	± 3	± 3	± 3	± 3	± 3	± 3	± 3	± 3	± 7	± 7	
Pregnancy Test – Urine or Serum (in appropriate study subjects)	X	X	X	X	X	X	X	X	X	X	X	X	X	X	
PT/INR and aPTT	X														
CBC with Differential	X	X	X	X	X	X	X	X	X	X	X	X	X	X	
Comprehensive Serum Chem Panel	X	X	X	X	X	X	X	X	X	X	X	X	X	X	
Urinalysis	X														

Trial Period:	Screening	Pembro Only	Doxorubicin/Pembrolizumab Combination							Pembrolizumab Only (repeat)				End of Treatment	
Treatment Cycle/Title:	Screening	1	2	3	4	5	6	7	8	9	10	11	At time of Discon	30 days post discon	
Scheduling Window (Days):	see section 7.1.5	± 3	± 3	± 3	± 3	± 3	± 3	± 3	± 3	± 3	± 3	± 3	± 7	± 7	
T3, FT4 and TSH	X	X	X	X	X	X	X	X	X	X	X	X	X	X	
Tumor Imaging ¹	X			X					X						
Archival Tissue Collection (slides)	X														
Correlative Studies Blood Collection	X	X	X			X			X				X		

1: Tumor imaging may be performed with a +/- 1-week window. Scans will take place per the schedule even if there are treatment delays.

7.0 TRIAL PROCEDURES

7.1 Trial Procedures

The Trial Flow Chart - Section 6.0 summarizes the trial procedures to be performed at each visit. Individual trial procedures are described in detail below. It may be necessary to perform these procedures at unscheduled time points if deemed clinically necessary by the investigator.

Furthermore, additional evaluations/testing may be deemed necessary by the Sponsor-Investigator and/or Merck for reasons related to subject safety. In some cases, such evaluation/testing may be potentially sensitive in nature (e.g., HIV, Hepatitis C, etc.), and thus local regulations may require that additional informed consent be obtained from the subject. In these cases, such evaluations/testing will be performed in accordance with those regulations.

7.1.1 Administrative Procedures

7.1.1.1 Informed Consent

The Investigator must obtain documented consent from each potential subject prior to participating in a clinical trial.

7.1.1.1.1 General Informed Consent

Consent must be documented by the subject's dated signature or by the subject's legally acceptable representative's dated signature on a consent form along with the dated signature of the person conducting the consent discussion.

A copy of the signed and dated consent form should be given to the subject before participation in the trial.

The initial informed consent form, any subsequent revised written informed consent form and any written information provided to the subject must receive the IRB/ERC's approval/favorable opinion in advance of use. The subject or his/her legally acceptable representative should be informed in a timely manner if new information becomes available that may be relevant to the subject's willingness to continue participation in the trial. The communication of this information will be provided and documented via a revised consent form or addendum to the original consent form that captures the subject's dated signature or by the subject's legally acceptable representative's dated signature.

Specifics about a trial and the trial population will be added to the consent form template at the protocol level.

The informed consent will adhere to IRB requirements, applicable laws and regulations and Sponsor-Investigator requirements.

